5.5.1 First supplementary estimand

The first supplementary estimand can be seen to assess the difference in response rates achieved regardless of permanent discontinuation of IMP and subjects becoming unblinded, if permanent discontinuation of IMP due to pandemic restrictions would not occur.

In accordance with [Panel 19](#), permanent discontinuation of IMP independent of pandemic restrictions will be addressed using the ‘treatment-policy’ strategy. Specifically, permanent discontinuation of IMP independent of pandemic restrictions will be ignored. The same strategies for addressing permanent discontinuation of IMP due to pandemic restrictions and unblinding of

THIS DOCUMENT CONTAINS CONFIDENTIAL INFORMATION AND MUST NOT BE COPIED OR MADE AVAILABLE TO ANY THIRD PARTY WITHOUT THE PRIOR WRITTEN CONSENT OF THE LEO PHARMA GROUP

subjects will be used, and missing data will be handled in the same way as for the main analysis of the primary estimand, with the exceptions that:

- Data collected from subjects who have permanently discontinued IMP independently of pandemic restrictions prior to Week 16 will be included when performing Step no. 1 of the multiple imputation method.
- Step no. 2 of the multiple imputation method will not be carried out.

These exceptions are introduced to align with the ‘treatment policy’ strategy for addressing permanent discontinuation of IMP independent of pandemic restrictions, which simply ignores treatment discontinuations of that nature. [Panel 20](#) summarises the procedure.

Panel 20. ‘Hypothetical’ strategy for addressing permanent discontinuation of IMP due to pandemic restrictions and handling of missing data in the main analysis of the first supplementary estimand for the primary endpoint

Step no.	Description	Subjects in scope for imputation	Purpose
1	Impute PASI 100 response at Week 16 under MAR assumptions	Subjects who have permanently discontinued IMP due to pandemic restrictions prior to Week 16	‘Hypothetical’ strategy
		Subjects who have not permanently discontinued IMP due to pandemic restrictions prior to Week 16 and whose PASI score at Week 16 is missing	Handling of missing data

Abbreviations: IMP = investigational medicinal product; MAR = missing at random; PASI = Psoriasis Area and Severity Index, PASI 100 = 100% improvement from baseline in PASI score.

5.5.1.1 Main analysis

Inference will be based on the logistic regression model described in the main analysis of the primary estimand under the same assumptions.

THIS DOCUMENT CONTAINS CONFIDENTIAL INFORMATION AND MUST NOT BE COPIED OR MADE AVAILABLE TO ANY THIRD PARTY WITHOUT THE PRIOR WRITTEN CONSENT OF THE LEO PHARMA GROUP

5.5.1.2 Sensitivity analysis

Sensitivity analyses of this estimand will assess the robustness of the imputation method for subjects with missing data. The following imputation methods will be used as described in section 5.4.1.2.1:

- Non-responder imputation.
- ‘Delta-adjusted’ pattern-mixture model.

5.5.2 Second supplementary estimand

The second supplementary estimand can be seen to assess the difference in the rate of achieving response without permanently discontinuing IMP, if permanent discontinuation of IMP due to pandemic restrictions and unblinding of subjects would not occur.

The second supplementary estimand associated with the primary endpoint will use the same strategies for addressing intercurrent events as the primary estimand for binary endpoints based on subject assessments.

5.5.2.1 Main analysis

Inference will be based on the logistic regression model described in the main analysis of the primary estimand under the same assumptions.

5.6 Safety analysis

The analysis of safety will be based on the safety analysis set.

5.6.1 Adverse events

AEs will be coded during the course of the trial according to Medical Dictionary for Regulatory Activities (MedDRA). AEs will be presented by preferred term (PT) and primary system organ class (SOC).

For AEs, missing values will be treated as missing, except for causality, intensity, seriousness, onset date and outcome of AEs. A worst-case approach will be used: if causality is missing, the AE will be regarded as related to the IMP; if the intensity of an AE is missing, the AE will be regarded as severe; if seriousness is missing, the AE will be regarded as serious; if onset date is missing, it will be assumed to be the first day of administration of IMP; if outcome is missing, and no date of outcome is present, the outcome is regarded as ‘not recovered’.

THIS DOCUMENT CONTAINS CONFIDENTIAL INFORMATION AND MUST NOT BE COPIED OR MADE AVAILABLE TO ANY THIRD PARTY WITHOUT THE PRIOR WRITTEN CONSENT OF THE LEO PHARMA GROUP

Treatment-emergent AEs will be summarised; however, all AEs recorded during the course of the trial will be included in subject data listings. An event will be considered treatment-emergent if the onset occurred after the first administration of IMP or if the event started prior to the first administration of IMP and worsened in severity after the first administration of IMP. Please refer to the ADRG regarding details on imputation of treatment-emergent flagging when timing information is missing. The tabulations described in the following will only include the treatment-emergent events reported prior to or at the Week 28 visit. In each of the tabulations, AEs are defined by MedDRA preferred terms within primary SOC. Tabulations of treatment-emergent AEs will be presented for the following 2 scenarios:

- ‘While exposed to IMP’, defined as AEs occurring within 5 half-lives after the most recent date of IMP administration.
- ‘While in trial’, defined as all AEs observed during the duration of the trial, beginning from the date of randomisation.

An overall summary of the number and percentage of subjects reporting the event, along with the number of events and the event rate per 100 subject-years for any treatment-emergent AEs, deaths, SAEs, AEs leading to permanent discontinuation of IMP or withdrawal from trial, treatment-related AEs, and severe AEs will be presented. An overall graphically summary of AEs by seriousness, severity, outcome and permanent discontinuation of IMP will be presented using histograms.

The severity for each type of AE will be tabulated by treatment arm.

The causal relationship to IMP for each type of AE will be tabulated by treatment arm. Related AEs are defined as AEs for which the investigator has not described the causal relationship to IMP as ‘not related’. The number of events, subjects and the event rate per 100 subject-years for each type of related AE will be tabulated and presented. An overall summary of the most frequent AEs by PT ($\geq 5\%$ in any treatment group) will be presented. The most frequent AEs ($\geq 5\%$ in any treatment group) will be tabulated by SOC and PT, and will be presented by PT and severity using histograms. The most frequent non-serious AEs ($\geq 5\%$ in any treatment group) will also be tabulated by SOC and PT. The most frequent AEs ($\geq 5\%$ in any treatment group) will be presented by SOC using dot plots.

THIS DOCUMENT CONTAINS CONFIDENTIAL INFORMATION AND MUST NOT BE COPIED OR MADE AVAILABLE TO ANY THIRD PARTY WITHOUT THE PRIOR WRITTEN CONSENT OF THE LEO PHARMA GROUP

SAEs will be evaluated separately and a narrative for each will be given – an overall summary and tabulation by SOC and PT of SAEs will be presented. AEs leading to withdrawal from trial or permanent discontinuation of IMP will be tabulated and listed. Cumulative frequency plots of AEs, AEs leading to withdrawal from trial and AEs leading to permanent discontinuation of IMP will also be produced.

Other events involving IMP (medication error, misuse, and abuse of IMP) will be summarised.

5.6.2 Adverse events of special interest

The AESIs for the trial are classified as important identified and important potential risks (CTP Section 13.5.2). The AESI will be tabulated and listed by treatment arm according to the safety analysis set for the ‘while exposed to IMP’ and ‘while on trial’ scenarios. It has been recorded in the eCRF whether or not an adverse event is an adverse event of special interest.

5.6.3 Vital signs

Vital signs are tabulated as described in the CTP Section 14.3.9.3. In addition, vital signs will be summarised by protocol defined visit week and a shift table will be produced showing ‘low’, ‘normal’ and ‘high’ categories at baseline against those at the end of the treatment period. The normal ranges to use for this classification are provided in [Panel 21](#).

Panel 21. Normal ranges to be used for shift tables involving vital signs parameters

Parameter	Normal range
Body temperature	36°C – 38°C
Diastolic Blood Pressure	50 mmHg – 105 mmHg
Systolic Blood Pressure	90 mmHg – 180 mmHg
Pulse	50 beats/min – 120 beats/min

Abbreviations: °C = degree Celsius; min = minute; mmHg = millimeter of mercury.

5.6.4 Physical examination

Physical examinations will be listed by subject.

THIS DOCUMENT CONTAINS CONFIDENTIAL INFORMATION AND MUST NOT BE COPIED OR MADE AVAILABLE TO ANY THIRD PARTY WITHOUT THE PRIOR WRITTEN CONSENT OF THE LEO PHARMA GROUP

5.6.5 Clinical laboratory evaluation

Clinical laboratory evaluations are tabulated as described in the CTP Section 14.3.9.4. In addition, laboratory reference ranges will be tabulated. Maximum post-baseline values (including unscheduled visits) and end of treatment values of selected chemistry and hematology parameters will be summarised by thresholds. Means and mean changes from baseline will be presented graphically for selected chemistry and hematology parameters.

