DLQI ⁸		X	X			X		X		X		X	X	(X)	11.3.4.1
SF-36v2 ⁸		X	X			X		X				X	X	(X)	11.3.4.2
eDiary device hand-out and training		X													11.3.4
Pruritus NRS ⁹		<=Daily at home during entire treatment period using an eDiary device =>										X ¹⁰			11.3.4.3
Pain NRS ⁹		<=Daily at home during entire treatment period using an eDiary device =>										X ¹⁰			11.3.4.4

THIS DOCUMENT CONTAINS CONFIDENTIAL INFORMATION AND MUST NOT BE COPIED OR MADE AVAILABLE TO ANY THIRD PARTY WITHOUT THE PRIOR WRITTEN CONSENT OF THE LEO PHARMA GROUP

Visit	Screening	Treatment (induction) period										Early termination visit ² As soon as possible within 2 weeks after last IMP	Unscheduled visit, if applicable ³	References (protocol section)	
	1	2	3	4	5	6	7	8	9	10	11 (primary endpoint visit)				
Week	-4/-2 to 0	0	1	2	4	6	8	10	12	14	16				
Visit window (days) ¹	-	-	±3	±3	±3	±3	±3	±3	±3	±3	±3				
eDiary device return												(X) ¹¹		11.3.4	
Investigator assessments of safety															
Vital signs	X	X	X	X	X	X	X	X	X	X	X	X	X	11.4.1	
Physical examination	X	X										X	X	(X)	11.4.2
Body measurements ¹²	X	X										X	X	(X)	11.4.3
Biochemistry ¹³ , haematology ¹⁴ , urinalysis (urine dipstick) ¹⁵	X	X										X	X	(X)	11.4.4
Albumin-to-creatinine ratio (urinalysis) ¹⁶	(X)													(X)	11.4.4
Urine pregnancy test ¹⁷		X			X		X		X			X	X	(X)	11.4.4
Serum pregnancy test ¹⁷	X	(X)			(X)		(X)		(X)			(X)	(X)	(X)	11.4.4
AEs and SAEs	X	X	X	X	X	X	X	X	X	X	X	X	X	(X)	13
Patient-reported outcomes of safety															
C-SSRS ¹⁸	X	X	X	X	X	X	X	X	X	X	X	X	X	(X)	11.5.2
PHQ-8 ⁸	X	X	X	X	X	X	X	X	X	X	X	X	X	(X)	11.5.3
Concluding forms in the eCRF															
End-of-treatment form ¹⁹												X			11.6.1
End-of-trial form ²⁰												(X) ²⁰			11.6.2

THIS DOCUMENT CONTAINS CONFIDENTIAL INFORMATION AND MUST NOT BE COPIED OR MADE AVAILABLE TO ANY THIRD PARTY WITHOUT THE PRIOR WRITTEN CONSENT OF THE LEO PHARMA GROUP

Footnotes to this panel are found below [Panel 3](#).

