- 6) PP-PASI and PP-IGA to be completed for all subjects at Visits 1 and 2. Subsequently, only subjects with palmoplantar psoriasis at baseline (Visit 2) will be followed using the separate tools PP-PASI and PP-IGA.
- 7) Only subjects with genital psoriasis at baseline will be followed using the separate tool sPGA-G.
- 8) The DLQI, SF-36v2, and PHQ-8 questionnaires should be completed by the subject prior to the investigator, safety, and C-SSRS assessments. For the sequence of assessments to be performed at each visit, please see [Panel 8](#).
- 9) To be completed daily by the subject from screening onwards. The subject must bring the device at Visit 2 (Week 0, baseline) for site to collect it from subjects who do not meet randomisation criteria (screening failures). The eDiary must be returned to the site at the last visit (e.g. final visit at Week 28 or early termination visit).
- 10) Must be completed at the early termination visit, if not already done at home before the visit.
- 11) The eDiary device return is marked '(X)' since this is optional depending on the subject's willingness to continue with all the remaining visits and assessments.
- 12) Height and weight. Height is only measured at screening.
- 13) Sodium, potassium, calcium, bicarbonate, albumin, blood urea nitrogen, creatinine, uric acid, total bilirubin, alkaline phosphatase, aspartate aminotransferase, alanine aminotransferase, C-reactive protein, cholesterol, low density lipoprotein (LDL) cholesterol, high density lipoprotein (HDL) cholesterol, triglycerides, and glucose. At Visit 1 (screening), the biochemistry assessments must also include estimated glomerular filtration rate (eGFR).
- 14) Red blood cell count, haemoglobin, haematocrit, platelets, white blood cell count, and differential (absolute count and %): neutrophils, lymphocytes, monocytes, eosinophils, and basophils.
- 15) Specific gravity, pH, occult blood, protein, glucose, leucocyte esterase, and ketones. In case of abnormal dipstick results, a urine sample will be sent to the central laboratory for microscopic examination (leukocytes, erythrocytes, and casts).
- 16) In case of abnormal dipstick results at screening, a urine sample will be sent to the central laboratory for albumin-to-creatinine ratio.
- 17) Only women of childbearing potential. At screening, a serum pregnancy test is always performed. For other visits, if a urine pregnancy test is positive, a serum pregnancy test must be done to confirm the result.

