10.2 IMP discontinuation rules

10.2.1 Reasons for permanent discontinuation of IMP

When discontinuing IMP, either at the scheduled end-of-treatment visit or IMP is discontinued prematurely, the subject should be treated at the discretion of the investigator (Section 9.9).

Subjects will permanently discontinue IMP prematurely in the event of:

- Having shown no response (efficacy) after 16 weeks of treatment.
- Anaphylactic reaction or other severe systemic reaction to IMP injection.
- An AE or deterioration of an AE that, in the opinion of the investigator or sponsor's medical expert, contraindicates further IMP administration (e.g. Crohn's disease).
- Some cases of use of prohibited medication and treatment, see Section 9.7 for further details.
- Diagnosis of a malignancy during the trial, excluding carcinoma in situ of the cervix, or localised squamous or basal cell carcinoma of the skin.
- Evidence of pregnancy (positive serum pregnancy test).
- Any infection that is opportunistic, such as active tuberculosis and other infections whose nature or course may suggest an immunocompromised status.
- Any suicidal behaviour or suicidal ideation of category 4 or 5 according to the C-SSRS (the subject must be referred to a mental health professional).
- A PHQ-8 score of ≥ 15 corresponding to moderately severe-to-severe depression (the subject must be referred to a mental health professional).
- Any single measurement of ANC $< 0.50 \times 10^3/\mu\text{L}$.
- Severe laboratory abnormalities:
 - ALT and/or AST values $> 3 \times \text{ULN}$ with total bilirubin $> 2 \times \text{ULN}$ (unless elevated bilirubin is related to Gilbert-Meulengracht Syndrome).
 - Confirmed ALT and/or AST $> 5 \times \text{ULN}$ (for more than 2 weeks).

Refer to Section 10.3 for details on the handling of discontinuation of IMP or withdrawal of a subject, and to Section 4 for assessments to be performed in case of discontinuation of IMP.

THIS DOCUMENT CONTAINS CONFIDENTIAL INFORMATION AND MUST NOT BE COPIED OR MADE AVAILABLE TO ANY THIRD PARTY WITHOUT THE PRIOR WRITTEN CONSENT OF THE LEO PHARMA GROUP

Data to be recorded in the eCRF

The primary reason for permanent discontinuation of IMP must be recorded in the medical records and on the end-of-treatment form in the eCRF where the following options are available:

- Lack of efficacy.
- Adverse event.
- Withdrawal by subject.
- Lost to follow-up.
- Death.
- Pregnancy.
- Other.

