14.3.9.4 Clinical laboratory evaluation

The change in each of the laboratory parameters from baseline will be summarised by visit and treatment arm as mean, SD, median, minimum, and maximum values for the safety analysis set.

Laboratory parameters will be classified as ‘low’, ‘normal’, or ‘high’, depending on whether the value is below, within, or above the reference range, respectively. A shift table will be produced showing the categories at baseline against those at the end of treatment. Subjects with laboratory parameters outside the reference range will be listed. Reference ranges will be listed in the SAP.

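### SAP 5.6.5 tabulates haematology by the maximum post-baseline value, so a low count that recovers while the subject stays on IMP enters no threshold or shift table

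*SAP*

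**What the plan says.** SAP 5.6.5 first takes over the protocol's tables: "Clinical laboratory evaluations are tabulated as described in the CTP Section 14.3.9.4". It then adds a threshold summary: "Maximum post-baseline values (including unscheduled visits) and end of treatment values of selected chemistry and hematology parameters will be summarised by thresholds". It does not list the selected parameters, give the thresholds, or define the end-of-treatment value.

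Protocol 14.3.9.4 plans three outputs:
- Changes from baseline, "summarised by visit and treatment arm as mean, SD, median, minimum, and maximum values".
- A low/normal/high classification: "A shift table will be produced showing the categories at baseline against those at the end of treatment".
- A listing: "Subjects with laboratory parameters outside the reference range will be listed".

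Neither document plans a minimum or a worst post-baseline category for any laboratory parameter.

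The haematology panel in the notes to protocol Panels 2 and 3 includes "white blood cell count, and differential (absolute count and %): neutrophils, lymphocytes, monocytes, eosinophils, and basophils", along with haemoglobin and platelets. Scheduled post-baseline haematology is at Weeks 16 and 28, plus the early termination visit and optional unscheduled visits.

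**The concern.** A post-baseline maximum is the right summary where high values are harmful, as with ALT, AST and bilirubin. SAP 5.6.5 applies the same rule to haematology, where the usual safety question is how far a count fell. The protocol treats ANC this way throughout. Section 8.3 excludes subjects below 2.00, section 10.2.1 stops IMP on a single value below 0.50, and section 10.2.2 suspends IMP for 0.50 to 1.5 with fever.

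Including unscheduled visits makes matters worse for these parameters. A repeat sample can only leave the maximum unchanged or raise it, so the recheck that documents recovery takes the subject out of the count. At stake is a by-arm count of subjects whose neutrophils or other counts fell below a limit on treatment, in a trial that has safety comparison among its objectives.

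**Working it through.** No figure in the plan needs reproducing. The check applies the planned rules to example subjects.

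**Rules.** For post-baseline values x1, ..., xk and a lower limit c:
- Maximum rule: flagged if max(x) < c, which requires every value to be below c.
- End-of-treatment rule: flagged if the end-of-treatment value is below c.
- Shift table: low if the end-of-treatment value is below the laboratory's lower reference limit.
- Minimum rule (the alternative): flagged if min(x) < c, which requires only one value below c.

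**Inputs.** The cut points 0.50 and 1.5 x10^3/uL come from protocol 10.2.1 and 10.2.2. A lower reference limit of 2.0 is assumed for the shift table. The ANC paths are illustrative: normal at baseline, no fever, IMP continued. For these completers the end-of-treatment value is taken to be Week 28, the end of the treatment period and the visit at which Panel 3 schedules the end-of-treatment form.

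| Path | Post-baseline ANC | Maximum (< 1.5?) | End of treatment (< 1.5?) | Shift table | Minimum (< 1.5?) |
|---|---|---|---|---|---|
| 1 | Week 16 0.9; Week 28 3.5 | 3.5 (no) | 3.5 (no) | normal | 0.9 (yes) |
| 2 | Week 16 1.2; unscheduled 1.4; Week 28 3.0 | 3.0 (no) | 3.0 (no) | normal | 1.2 (yes) |
| 3 | Week 16 3.9; Week 28 1.1 | 3.9 (no) | 1.1 (yes) | low | 1.1 (yes) |
| 4 | Week 16 1.1; Week 28 1.0 | 1.1 (yes) | 1.0 (yes) | low | 1.0 (yes) |

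Paths 1 and 2, the recovered cases, are flagged by none of the planned tables. Their shift result holds for any lower reference limit up to 3.0, the smaller of their two end-of-treatment values. Path 3 is missed by the maximum but caught by the end-of-treatment value and the shift table. Path 4 is caught by all. The minimum flags all four.

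**A value below 0.50 is a different case.** Take Week 16 3.8, unscheduled 0.45, Week 28 3.6. The maximum is 3.8 and the minimum 0.45, so the maximum rule misses it. But section 10.2.1 requires IMP to stop, and section 10.3 then asks for an early termination visit within 2 weeks of the last IMP, at which haematology is scheduled. If IMP is stopped at a scheduled visit, the early termination assessments are done at that visit. The end-of-treatment value may therefore be a sample that is still low, in which case the threshold and shift tables would count it. The documents do not settle which sample is used, so this path is not relied on.

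**The case against.** Several objections carry weight.

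- **Recovered low values are reported elsewhere.** A reader might infer that a recovered neutropenia goes unreported, or that the arms' neutropenia comparison as a whole is understated. The documents do not support that. Every subject outside the reference range is listed. A low Week 16 value can show in that visit's minimum change. A new clinically significant laboratory abnormality is reported as an AE (protocol 11.4.4.2 and Appendix 1), and AEs are tabulated by arm, preferred term and severity (protocol 14.3.9.1, SAP 5.6.1). This stands. What remains uncounted by arm is a fall not judged clinically significant that recovers on treatment.
- **The stopping-level event may be caught.** A reader might also infer that a fall below 0.50, or every recovered low value, is missed. As shown in the working, that depends on an undefined end-of-treatment value, so the inference is too strong.
- **Parameters and thresholds are unnamed.** Neutrophils may not be among the selected parameters. This stands as a limit on the claim. If they are not selected, though, no threshold table covers them and the shift table alone still omits the recovered value.
- **Maximum may be loose wording for worst.** This is not persuasive. SAP section 1 says its detail should allow the analyses to be reproduced, and a programmer following 5.6.5 would take a maximum. Where the protocol wants each subject's worst value, as for the C-SSRS and PHQ-8, it asks for the most severe.
- **The stakes are small.** The table is descriptive and neutropenia is not an AESI. The trial ended ahead of schedule, and the raw values are retained, so a minimum can be tabulated later. This stands and sets the severity.

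**Conclusion.** The point holds in a narrow form and is minor. For haematology parameters where low is harmful, the threshold rule points the wrong way. A low Week 16 or unscheduled value that recovers while the subject stays on IMP is counted in no threshold or shift table. The planned rules can miss such values but cannot over-count them. How many subjects this affects cannot be estimated from the documents.

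The conclusion rests on two assumptions. First, the end-of-treatment value for a completer is the Week 28 sample. If it were instead the last sample up to the final injection at Week 26, a low Week 16 value could be caught, and a low value at Week 28 alone would be missed by the end-of-treatment rule. Second, the selected haematology parameters include at least one where low is harmful. If none is selected, the planned tables still give no count of recovered low values, because no threshold table would cover these parameters at all.

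**What to change.** In SAP 5.6.5, summarise by thresholds the minimum post-baseline value, including unscheduled visits, for neutrophils, leukocytes, lymphocytes, platelets and haemoglobin. Include the protocol's existing ANC limits, 0.50 and 1.5 x10^3/uL, among the table thresholds. Keep the maximum for ALT, AST, bilirubin and other parameters where high is harmful. The same edit can name the selected parameters and their thresholds, and say which sample is the end-of-treatment value for completers and for subjects who stop IMP early.

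The core change costs one SAP sentence and a minimum in place of a maximum in one table program. It needs no new data and changes no clinical rule.
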